4.1. Primary Objectives

The primary objectives of this study are:

- to characterize the safety profile and tolerability of each combination, LY3022855 with durvalumab (MEDI4736) and LY3022855 with tremelimumab, in the treatment of patients with advanced solid tumors
- to define a recommended Phase 2 dose (RP2D) for each combination, LY3022855 with durvalumab and LY3022855 with tremelimumab, in the treatment of patients with advanced solid tumors

4.2. Secondary Objectives

The secondary objectives of this study are:

- to document the antitumor activity of each combination, LY3022855 with durvalumab and LY3022855 with tremelimumab, in the treatment of patients with advanced solid tumors.
- to assess the development of antibodies against LY3022855, durvalumab, and tremelimumab (immunogenicity)
- to characterize the single-dose and multiple-dose pharmacokinetics (PK) of LY3022855 in combination with either durvalumab or tremelimumab, and the single-dose and multiple-dose PK of durvalumab and tremelimumab, each in combination with LY3022855

4.3. Exploratory Objectives

- to explore the effects of the combinations of LY3022855 with durvalumab or tremelimumab in the treatment of patients with advanced solid tumors on changes in immune cell subset frequency and activation
- to explore the pharmacodynamic profile of each combination, LY3022855 with durvalumab and LY3022855 with tremelimumab, in the treatment of patients with advanced solid tumors
- to explore cellular and molecular markers potentially associated with safety and antitumor and biological activity of the combination of LY3022855 with durvalumab or tremelimumab, in the treatment of patients with advanced solid tumors

5. Summary of Study Design

Study I5F-MC-JSCC is a multicenter, nonrandomized, open-label, dose-escalation Phase 1a/1b study of LY3022855 in combination with either durvalumab or tremelimumab, in patients with advanced solid malignancies. In Part A, enrollment to the tremelimumab cohorts may potentially start after the enrollment to the durvalumab cohorts. Eligible patients will receive treatment as follows:

- LY3022855 once weekly, in combination with:
 - durvalumab once every 2 weeks
 - OR
 - tremelimumab once every 4 weeks; after 6 doses, tremelimumab once every 12 weeks until discontinuation

The study will be conducted in 2 parts:

- Part A – Phase 1a, dose escalation
- Part B – Phase 1b, disease-specific expansion

The following description applies to each combination therapy.

During Part A, patients will be enrolled in a 3+3 design to increasing dose levels, as tolerated. In the event dose-limiting toxicities (DLTs) prevent further dose escalation, exploration of additional dosages between the highest dose tested and the previously identified safe dosage may be explored after further discussion with the investigators, Sponsor, and collaborator. Once a maximum tolerated dose (MTD) has been identified for each combination, enrollment to Part B (5 disease-specific expansion cohorts of 20 patients per cohort) will begin. The non-small cell lung cancer cohort will consist of a minimum of 10 patients with disease refractory to checkpoint therapy and a minimum of 6 patients with disease relapsed on prior checkpoint therapy. Patients in Part B will be treated at the MTD for a given combination, unless otherwise specified by the Sponsor. Upon completion of Part B, which is intended to confirm tolerability of a combination dose, the RP2D will be declared/defined. For patients with melanoma, assignment to the durvalumab or the tremelimumab combination cohort will be made by the Sponsor after consultation with the treating investigator, based upon the patient's medical history as well as the availability of open slots.

All patients enrolled to all cohorts of Part A or to the ovarian cancer cohort of Part B will undergo mandatory attempted pretreatment and on-treatment (6-8 weeks after starting study treatment) tumor core needle or excisional biopsies.

Figure JSCC.5.1 presents the overall study design. Figure JSCC.5.2 presents the schema for an individual patient with regard to timing of tumor tissue biopsies.

5.1. Determination of Sample Size

Up to approximately 178 patients (78 [Part A] + 100 [Part B]) may be enrolled in this multicenter, nonrandomized, open-label Phase 1a/1b study of LY3022855.

The sample size for Part A will be determined primarily by the incidence of DLTs prior to establishing the MTDs in Part A. The anticipated sample size for Part A ranges from approximately 12 to 36 patients in the combination of LY3022855 plus durvalumab and approximately 12 to 42 patients in the combination of LY3022855 plus tremelimumab. In each cohort of Part B, approximately 20 patients will be enrolled. Patients in Part A (dose-finding) who receive all doses of study treatment for Cycle 1 (DLT-evaluation period) or who are discontinued from the study due to DLTs will be considered evaluable for the assessment of a dose level. Nonevaluable patients in Part A may be replaced to ensure that enough patients complete 1 cycle of therapy at each dose level for Part A, unless accrual to that cohort has stopped due to a DLT. The sample size of Part B has been selected to allow adequate assessment of safety and tolerability of LY3022855 in combination with durvalumab or tremelimumab at the recommended dose level and can provide adequate precision for the estimated incidence rate of the following quantities of interest: (1) patients having a specified adverse event (AE), or (2) patients showing a response (partial response [PR]/complete response [CR]) to treatment. Example point estimates of incidence rates and corresponding 2-sided 95% confidence intervals (CI) are summarized in [Table JSCC.5.1](#). The values are provided as a reference for estimation rather than a basis of any decision criteria. The RP2D may be revised based on the safety data obtained in Part B (Iasonos and O’Quigley 2013).

Table JSCC.5.1. Estimated Incidence Rate and 2-Sided 95% CI

Number of Cases (N=20)	Estimated Incidence Rate	95% CI ^a	
		Lower Limit	Upper Limit
0	0.0	0.0	0.17
5	0.25	0.09	0.49
10	0.50	0.27	0.73
15	0.75	0.51	0.91

Abbreviations: CI = confidence interval; N=number of patients.

a 95% Clopper-Pearson interval for binomial distribution with sample size of 20.

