- b Patients in Part A who receive all doses of study treatment for Cycle 1 (DLT-evaluation period) will be considered evaluable for the assessment of a dose level, provided it can be documented whether the patient did or did not experience a DLT within 28 days of Cycle 1, Day 1.

Treatment Arms and Duration:

For both Parts A and B, the planned duration of treatment is not fixed; patients will remain on study until they fulfill one of the criteria for study discontinuation.

Part A (Dose Escalation) Dose Regimens for the LY3022855-plus-Durvalumab Combination, by Cohort

Cohort	LY3022855		Durvalumab	
	Dose (mg)	Frequency	Dose (mg)	Frequency
D1a	25	QW	750	Q2W
	D1b ^a	25 Days 1, 8, and 15 of each cycle	750	Q2W
	D1c	25 Q2W	750	Q2W
D2a	50	QW	750	Q2W
	D2b ^a	50 Days 1, 8, and 15 of each cycle	750	Q2W
	D2c	50 Q2W	750	Q2W
D3a	75	QW	750	Q2W
	D3b ^a	75 Days 1, 8, and 15 of each cycle	750	Q2W
	D3c	75 Q2W	750	Q2W
D4a	100	QW	750	Q2W
	D4b ^a	100 Days 1, 8, and 15 of each cycle	750	Q2W
	D4c	100 Q2W	750	Q2W

Abbreviations: QW = weekly; Q2W = every 2 weeks.

Note: A cycle is defined as 28 days (4 weeks). QW refers to dosing on Days 1, 8, 15, and 22 of each cycle; Q2W refers to dosing on Days 1 and 15 of each cycle.

^a Enrollment to the Dnb cohort will occur only if ≥ 2 DLTs are observed after Cycle 1, Day 21 of the corresponding Dna cohort.

Part A (Dose Escalation) Dose Regimens for the LY3022855-plus-Tremelimumab Combination, by Cohort

Cohort	LY3022855		Tremelimumab	
	Dose (mg)	Frequency	Dose (mg)	Frequency ^a
T1a	50	QW	75	Q4W
	T1b ^b	50 Days 1, 8, and 15 of each cycle	75	Q4W
	T1c	50 Q2W	75	Q4W
T2a	100	QW	75	Q4W
	T2b ^b	100 Days 1, 8, and 15 of each cycle	75	Q4W
	T2c	75 Q2W	75	Q4W
T3a	100	QW	225	Q4W
	T3b ^b	100 Days 1, 8, and 15 of each cycle	225	Q4W
	T3c	100 Q2W	225	Q4W
	T3d	75 QW	225	Q4W
T4a	100	QW	750	Q4W
	T4b	100 Q2W	750	Q4W
	T4c	100 Days 1, 8, 15 of each cycle	750	Q4W
	T4d	75 QW	750	Q4W

Abbreviations: QW = weekly; Q2W = every 2 weeks; Q4W = every 4 weeks.

Note: A cycle is defined as 28 days (4 weeks). QW refers to dosing on Days 1, 8, 15, and 22 of each cycle; Q2W refers to dosing on Days 1 and 15 of each cycle; Q4W refers to dosing on Day 1 of each cycle.

^a After 6 doses, tremelimumab to be dosed once every 12 weeks until discontinuation.

^b Enrollment to the Tnb cohort will occur only if ≥ 2 DLTs are observed after Cycle 1, Day 21 of the corresponding Tna cohort.

Treatment for Part B (Disease-Specific Dose Expansion Cohorts): LY3022855 plus Durvalumab

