7.2.2.1. Dose-Limiting Toxicity Determination and Maximum Tolerated Dose Definition

Dose-limiting toxicity is defined as an AE that is at least possibly related to the study drug(s) and that occurs during Cycle 1 (the DLT-evaluation period) and does not improve to the National Cancer Institute's (NCI) Common Terminology Criteria for Adverse Events (CTCAE) v4.0 (CTEP 2009) Grade ≤ 2 (unless stated otherwise), despite medical management, including steroids (if applicable). Toxicity that is clearly and directly related to the primary disease or to another etiology is excluded from this definition. The following are considered DLTs, unless noted otherwise:

- Grade 4 neutropenia lasting ≥ 7 days
- Grade 3 or 4 neutropenia complicated by fever or infection of any duration
- Any Grade 4 thrombocytopenia
- Any Grade 3 thrombocytopenia complicated by hemorrhage
- Any Grade 3 or 4 anemia

- Grade 3 or 4 nonhematologic toxicity, including:
 - any Grade 4 irAE
 - any Grade 3 or 4 colitis
 - any Grade 3 or 4 noninfectious pneumonitis irrespective of duration
 - any Grade 3 irAE, excluding colitis or pneumonitis, that does not downgrade to Grade 2 within 3 days after onset of the event despite optimal medical management including systemic corticosteroids or does not downgrade to Grade ≤ 1 or baseline within 14 days
 - any Grade 3 or 4 non-irAE except as noted for transaminases, bilirubin, lipase, or amylase below
 - any liver transaminase elevation $>8 \times$ institutional ULN or total bilirubin (TB) $>5 \times$ institutional ULN
 - creatine kinase elevation $>8 \times$ ULN
- Any Grade 2 pneumonitis that does not resolve to Grade ≤ 1 within 3 days of the initiation of maximal supportive care

The DLT definition excludes the following conditions:

- Grade 3 fatigue lasting ≤ 7 days
- Grade 3 endocrine disorder (thyroid, pituitary, and/or adrenal insufficiency) that is managed with or without systemic corticosteroid therapy and/or hormone replacement therapy and the patient is asymptomatic
- Grade 3 inflammatory reaction attributed to a local antitumor response (for example, inflammatory reaction at sites of metastatic disease, lymph nodes, etc)
- Concurrent vitiligo or alopecia of any AE grade
- Grade 3 IRR (first occurrence and in the absence of steroid prophylaxis) that resolves within 6 hours with appropriate clinical management

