7.6. Treatment Compliance

Study treatment will be administered I.V. at the investigational site, under the direction of the investigator. As a result, a patient's compliance with study drug administration is ensured. Patients should attend scheduled clinic visits and must comply with study criteria under their control. Deviation(s) from the prescribed dosage regimen should be recorded on the eCRF.

7.6.1. *Evaluable Patients*

Patients in Part A who receive all doses of study treatment for Cycle 1 (DLT-evaluation period) will be considered evaluable for the assessment of a dose level, provided it can be documented whether the patient did or did not experience a DLT within 28 days of Cycle 1, Day 1.

Conversely, any patient in Part A who is discontinued from the study before completing one cycle of study treatment will be deemed nonevaluable for assessment of a dose level, unless they experience a DLT prior to withdrawal. Nonevaluable patients may be replaced to ensure that enough patients complete one cycle of therapy at each dose level for Part A, unless accrual to that cohort has stopped due to a DLT.

Patients who are not evaluable for PK but who complete one cycle of therapy may be replaced upon consultation with the investigator(s) and the sponsor's CRP/CRS to ensure adequate PK data, unless accrual to that cohort has stopped due to a DLT.

Note that the concept of "evaluable" (and, thus, replacement of patients) does not apply to patients in Part B.

8. Safety, Pharmacokinetic, Pharmacodynamic, and Efficacy Data Collection

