6.2. Handling of Dropouts or Missing Data

Missing data, except dates, will not be imputed. Historical data such as historical diagnosis, historical illness, preexisting conditions, and prior therapies should be collected in a sufficiently informative way. For example, in order to be considered as historical illness, events occurring in the same year as study entry should have at least a known month and year for the end date, while events occurring in previous years should have at least a known year for the end date. When dates need to be imputed, missing days will be replaced with 15th of the month and missing day/month with 01 July.

In the following situations of Part A, patients will be considered nonevaluable and may be replaced to ensure that enough patients complete 1 cycle of therapy at each dose level, unless accrual to that cohort has stopped due to a DLT:

1. Any patient who is discontinued from the study before completing 1 cycle of therapy unless they experience a DLT prior to withdrawal
2. Patients who are not evaluable for PK, but who complete 1 cycle of therapy

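### SAP 5.1 and 6.2 do not match Protocol 7.6.1 on which Part A patients count in the 3+3 decision, so a first DLT can drop out of the dose-level count

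*SAP*

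**What the plan says.** Four places define who counts.

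- **SAP 5.1** names two evaluable groups: Part A patients who "receive all doses of study treatment for Cycle 1 (DLT-evaluation period) or who are discontinued from the study due to DLTs". The next sentence lets nonevaluable patients be replaced "unless accrual to that cohort has stopped due to a DLT".
- **SAP 6.2** lists two kinds of nonevaluable, replaceable patient. Item 1 is "Any patient who is discontinued from the study before completing 1 cycle of therapy unless they experience a DLT prior to withdrawal". Item 2 is "Patients who are not evaluable for PK, but who complete 1 cycle of therapy". Item 2 has no DLT exception.
- **Protocol 7.6.1** counts patients who received every Cycle 1 dose and whose DLT status is documented. A patient who leaves before completing the cycle "will be deemed nonevaluable for assessment of a dose level, unless they experience a DLT prior to withdrawal". On PK it says: "Patients who are not evaluable for PK but who complete one cycle of therapy may be replaced upon consultation". The stated purpose is adequate PK data; these patients are not called nonevaluable for the dose level.
- **Protocol synopsis, Number of Patients, footnote b** gives only the all-doses rule: patients "who receive all doses of study treatment for Cycle 1 (DLT-evaluation period) will be considered evaluable for the assessment".

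On replacement itself, Protocol 7.6.1 and the SAP say nonevaluable patients may be replaced. Protocol 10.1 and the synopsis say they will be.

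**The concern.** Under Protocol 7.2.2.2 a level clears on 0 of 3 or 1 of 6 and stops on 2 or more. One patient moved out of the count can change that decision. SAP 5.1 makes the reason for leaving decisive, and its all-doses test is most likely to fail in patients whose toxicity interrupted dosing. The accrual clause does not protect a first DLT, because 1 DLT in 3 leads to more enrolment at that level, not to a stop.

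In the 'a' cohorts a lost DLT favours escalation, and the MTD found there sets the Part B dose. In the 'c' cohorts the direction is not general. A missed DLT could leave D3c as the MTD rather than its fallback D2a, but per cycle D3c gives 75 mg × 2 = 150 mg of LY3022855 and D2a gives 50 mg × 4 = 200 mg.

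**Working it through.** **1. The plan's own Part A figures.** Four 'a' levels × 3 = 12 is the minimum for each combination. The durvalumab maximum is 4 × 6 + 2 × 6 = 36, the tremelimumab maximum is 4 × 6 + 3 × 6 = 42, and the total is 78. All agree with SAP 5.1 and Protocol 10.1. They are not in dispute.

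**2. The rules side by side, for a patient with a Cycle 1 DLT.**

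| Patient | SAP 5.1 | SAP 6.2 | Protocol 7.6.1 |
|---|---|---|---|
| A. Misses a dose, leaves during Cycle 1 for another reason | in neither evaluable group | kept (item 1) | kept |
| B. Misses a dose, stays on study | in neither evaluable group | not listed | not classified |
| C. Completes Cycle 1 with all doses, PK not evaluable | evaluable | nonevaluable (item 2) | evaluable; replaceable for PK only |

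A and C are conflicts. B is a gap.

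**3. Can patient B arise?** Yes. Protocol 7.2.2.1 counts as a DLT "any Grade 3 irAE, excluding colitis or pneumonitis, that does not downgrade to Grade 2 within 3 days after onset of the event". For a Grade 3 rash, Attachment 7 holds treatment and requires permanent discontinuation only if there is no improvement within 30 days. Protocol 7.2.1.1 skips an LY3022855 dose that falls beyond the 3-day window. Protocol 7.2.2.1 lets DLT patients continue by agreement. Such a patient can have a DLT, miss a Cycle 1 dose and remain on study.

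**4. Worked cases.** One DLT in the first 3 requires expansion to 6. If that patient is replaced by one without a DLT, 1 of 4 treated patients had a DLT but the level reads 0 of 3 and escalates. Likewise 2 of 6 stops escalation; with one of the two replaced by a patient without a DLT it reads 1 of 6 and escalates.

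**5. Illustration of size.** Let p be the true DLT rate, q = 1 − p, and f the share of DLT patients replaced. The documents give no value for f, so it is an assumption. Let p′ = p(1 − f) / [p(1 − f) + q] and q′ = 1 − p′. The probability that an 'a' level clears depends on how the accrual clause is read:

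- R1, no accrual limit: q′³ + 3p′q′⁵
- R2, a DLT after one counted DLT cannot be replaced: q′³ + p′(q⁵ + q′q⁴ + q′²q³)
- R3, two observed DLTs stop accrual, counted or not: q³ + 3p(1 − f)q⁵ + 3pf·q³

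With f = 0 all three reduce to q³ + 3pq⁵. At p = 0.33 this is 0.3008 + 0.1337 = 0.434.

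At p = 0.33 and f = 0.25, p′ = 0.2475 / 0.9175 = 0.270:

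- R1: 0.3894 + 0.1680 = 0.557
- R2: 0.3894 + 0.1194 = 0.509
- R3: 0.3008 + 0.1002 + 0.0744 = 0.475

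| p | f | R1 | R2 | R3 |
|---|---|---|---|---|
| 0.33 | 0 | 0.434 | 0.434 | 0.434 |
| 0.33 | 0.10 | 0.480 | 0.461 | 0.451 |
| 0.33 | 0.25 | 0.557 | 0.509 | 0.475 |
| 0.33 | 0.50 | 0.714 | 0.614 | 0.516 |
| 0.40 | 0 | 0.309 | 0.309 | 0.309 |
| 0.40 | 0.25 | 0.428 | 0.383 | 0.351 |

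A separate exact recursion, in which only the first DLT patient at a level can be left out, gives 0.460, 0.498 and 0.561 at p = 0.33 for f = 0.10, 0.25 and 0.50. The direction is the same. Replacement of patients without a DLT is left out because the fix does not change it.

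**The case against.** The strongest reply is that the operative rule has no evaluability filter. Protocol 7.2.2.2 acts on observed DLTs, and Table JSCC.3 counts patients who experience one in Cycle 1. Escalation needs documented agreement of the investigator, the sponsor and the collaborator, and SAP 6.8.2 still summarises every DLT. A team that knows of a DLT would have to put a sample-size sentence in the SAP ahead of the protocol's own table. This stands as a limit: the event is not lost from safety reporting, and its loss from the dose-level count is possible, not certain.

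It can also be said that SAP 5.1 never uses the word 'only', so SAP 6.2 item 1 could be read as governing. That reading is available. But the sentence in SAP 5.1 serves as the definition, since the next one makes nonevaluable patients replaceable, and the two SAP sections then give different answers for patient A. Item 2 of SAP 6.2 cannot be read away.

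Three further points are fair. Patient B is a gap, not a mismatch. Patient C matters only if PK loss is related to DLT or replacement is selective, and nothing in the documents suggests either. The share f is assumed, and the size depends on the model: under R3 with f = 5% the probability moves only from 0.434 to 0.443.

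**Conclusion.** The concern holds. SAP 5.1 conflicts with Protocol 7.6.1 and with SAP 6.2 item 1. SAP 6.2 item 2 conflicts with Protocol 7.6.1 and with SAP 5.1. Neither document classifies a DLT patient who misses a dose and stays on study. Followed literally, the rules allow a DLT patient to be replaced and left out of a count decided by single patients, and in the 'a' cohorts the error runs towards escalation. How often this would happen cannot be determined from the documents; the probabilities above show only how sensitive the 3+3 decision is to it. The point should be fixed, but it does not undermine the design.

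**What to change.** 1. Put one definition in Protocol 7.6.1 and cross-refer to it from synopsis footnote b, SAP 5.1 and SAP 6.2: any Part A patient with a Cycle 1 DLT is evaluable and counted at that dose level, whatever doses were missed, whether or why the patient left, and whatever the PK status.
2. Delete item 2 from the nonevaluable list in SAP 6.2. State that a PK replacement adds PK data and never takes a patient out of the DLT count.
3. Optionally, list replaced patients with reason and DLT status at each cohort review.

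The cost is one definition, three cross-references and one deleted list item. Cases A and C can be settled in the SAP alone. Case B needs words in Protocol 7.6.1 and so belongs in a protocol amendment. No dose, DLT criterion, planned evaluable sample size or rule for patients without a DLT changes.

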5.2. Method of Assignment to Treatment

In Part A of dose escalation (Phase 1a), patients who meet all criteria for enrollment will be assigned to receive protocol-defined treatment in this study. Before each patient’s enrollment into the study, an eligibility check must be conducted between the investigational site and the Lilly clinical research personnel to confirm that each patient meets all enrollment criteria. Upon confirmation of eligibility, the Sponsor will confirm the dose and identification number assignment and cohort for each patient.

If investigators have eligible patients who have consented concurrently, more than 3 patients may be entered at a particular dose level, provided that accrual has not ceased due to excessive toxicity. This enrollment procedure is allowed because of the advanced disease state of this patient population and the screening involved in defining eligibility. This event should be approved by the Sponsor following discussions with the investigators.

In Part B of disease-specific expansion (Phase 1b), a patient who meets all criteria for enrollment will be assigned (by the Sponsor) to a treatment cohort, based on the patient's diagnosis at baseline.

[figure not shown]

Figure JSCC.5.1. Illustration of Study JSCC study design.

[figure not shown]

Figure JSCC.5.2. Schema for an individual patient with regard to timing of tumor tissue biopsies.

6. A Priori Statistical Methods

6.1. General Considerations

Statistical analysis of this study will be the responsibility of Eli Lilly and Company (Lilly). The interpretation of the study results will be the responsibility of the investigator with the Lilly clinical research physician (CRP)/clinical research scientist (CRS), pharmacokineticist, and statistician. The CRP/CRS and statistician will also be responsible for the appropriate conduct of an internal review for both the final study report and any study-related material to be authorized by Lilly for publication.

The analyses for this study will be descriptive; no p-values will be calculated. Data analyses will be provided by cohort and treatment whenever appropriate. For continuous variables, summary statistics will include number of patients, mean, median, standard deviation, minimum, and maximum. Categorical endpoints will be summarized using number of patients and percentages. Exploratory analyses of the data that are not described in the protocol will be conducted as deemed appropriate.

Any change to the data analysis methods described in the protocol will require an amendment ONLY if it changes a principal feature of the protocol. Any other change to the data analysis methods described in the protocol and the justification for making the change will be described in the clinical study report (CSR).

The following data handling conventions will be used in the analysis (see [Table JSCC.6.1](#)).

Table JSCC.6.1. Data Handling Conventions

Term	Definition or Rule
Relative Study Day	If assessment is on or after date of first dose then $(\text{date of assessment}) - (\text{date of first study drug dose}) + 1$
	If assessment precedes first dose of drug then $(\text{date of assessment}) - (\text{date of first study drug dose})$
	There is no Study Day 0. Study Day 1 is the date of first dose and Study Day -1 is the day before the first dose.
Baseline	For change from baseline analyses, baseline value is defined as the last reported measure on or before the first dose date (prior to the dose administration), unless otherwise specified. For change from baseline within a cycle, baseline value is defined as the measure prior to the first dose of that cycle, unless otherwise specified.
Entered	Patients who have signed the informed consent form directly or through their legally acceptable representatives
Enrolled	Patients who have been assigned to a study treatment and have received at least 1 dose of study treatment

